3.2.2 Overall Survival

Overall Survival is defined as the time from the date of randomisation until death due to any cause (i.e. date of death or censoring – date of randomisation + 1). Any patient not known to have died at the time of analysis will be censored based on the last recorded date on which the patient was known to be alive. This analysis will be based on the “date subject last known to be alive” variable which is recorded within the survival status module of the eCRF (SURVIVE module).

Note: Survival calls will be made in the week following the date of DCO for the analysis, and if patients are confirmed to be alive or if the death date is post the DCO date these patients will be censored at the date of DCO. If a patient has died but the date of death cannot be determined, then the patient will be censored based on the last recorded date on which the patient was known to be alive (although every effort needs to be made to determine the date of death). The status of ongoing, withdrawn (from the study) and “lost to follow-up” patients at the time of the final OS analysis should be obtained by the site personnel by checking the patient’s notes, hospital records, contacting the patient’s general practitioner and checking publicly-available death registries. If the patient has actively withdrawn consent to the processing of their personal data, the vital status of the patient can be obtained by site personnel from publicly-available resources where it is possible to do so under applicable local laws.

3.2.3 Time from randomisation to second progression

The time from randomisation to second progression (PFS2) is defined as the time from the date of randomisation to the earliest of the second progression event as assessed by the investigator or death (ie date of PFS2 event or censoring – date of randomisation + 1). The

date of second progression will be recorded by the investigator and defined according to local standard clinical practice and may involve any of objective radiological or symptomatic progression or death. The RECIST assessments will not be collected for assessment of PFS2. The date of the PFS2 assessment and investigator opinion of progression status (progressed or non-progressed) at each assessment will be recorded in the eCRF.

Second progression status will be reviewed every 8 weeks following the investigator assessment of the first objective progression and status recorded (until DCO2). Patients alive and for whom a second disease progression has not been observed should be censored at the last time known to be alive and without a second disease progression, ie, censored at the latest of the RECIST assessment or PFS2 assessment dates. If a patient progresses for the second time or dies after two or more missed visits, the patient will be censored for PFS2 at the time of the latest evaluable investigator – recorded assessment.

Censoring will need to be applied for some patients prior to the first progression and for others after the first progression, depending if the patient had a first progression at the time of analysis or not. The duration of two missed visits is depending on the respective visit schedule:

- If the patient was progression-free at the time of analysis, then patients will be censored as described for PFS (Section 3.2.1), i.e. using the latest RECIST scan.
- If the patient died in the absence of any progression after two or more missed visits, then the censoring visit rule as described for PFS (Section 3.2.1) needs to be applied.
- If a patient is alive and had only the first progression assessed at the time of analysis, then the censoring will be based on the latest investigator assessment of no progression in the follow-up phase. If there are no follow-up results recorded, then the date of the latest scan contributing to the investigator assessment of first progression will be used for censoring.
- If the patient had progressed once and then died or progressed for the second time after two or more visits, then those two or more missed visits equate to more than 18 weeks, since the patient is in the follow-up phase (16 weeks plus allowing an extra two weeks for early and late visits), i.e., if the latest follow-up assessment prior to second progression or death was more than 18 weeks ago, then the patient is censored with the date of this last investigator assessment. If no follow-up results are recorded, and the investigator assessment of first progression is more than 18 weeks ago, then the date of the latest scan contributing to this first progression assessment will be used for censoring.

3.2.4 Time to first subsequent therapy or death

As a supportive summary to PFS, TFST will be assessed at the 30-day follow-up visit following study treatment discontinuation and then every 8 weeks until DCO2 / every 12 weeks after DCO2, in line with survival follow-up visits. The TFST is defined as the time from randomisation to the earlier of first subsequent cancer therapy start date following study treatment discontinuation, or death (i.e. date of first subsequent cancer therapy/death or censoring – date of randomisation + 1). Any patient not known to have died at the time of the

analysis and not known to have had a further intervention of this type will be censored at the last known time to have not received subsequent cancer therapy, ie, the last follow-up visit where this was confirmed.

3.2.5 Time to second subsequent therapy or death

As a supportive summary to PFS2, TSST will be assessed at the 30-day follow-up visit following study treatment discontinuation and then every 8 weeks until DCO2 / every 12 weeks after DCO2, in line with survival follow-up visits. The TSST is defined as the time from randomisation to the earlier of the second subsequent cancer therapy start date following study treatment discontinuation, or death (i.e. date of second subsequent cancer therapy/death or censoring – date of randomisation + 1). Any patient not known to have died at the time of the analysis and not known to have had a further intervention of this type will be censored at the last known time to have not received second subsequent cancer therapy, ie, the last follow-up visit where this was confirmed.

3.2.6 Time to study treatment discontinuation or death

The TDT is defined as the time from randomisation to the earlier of the date of study treatment discontinuation or death (i.e. date of study treatment (olaparib/placebo) discontinuation/death or censoring – date of randomisation + 1). Any patient not known to have died at the time of analysis and not known to have discontinued study treatment will be censored based on the last recorded date on which the patient was known to be alive. Patients who were randomised but never exposed to study treatment will be censored at day 1.

3.2.7 Best objective response

Best objective response (BoR) is calculated based on the overall visit responses from each RECIST assessment (Table 6). It is the best response a patient has had following randomisation but prior to starting any subsequent cancer therapy and prior to RECIST progression or the last evaluable assessment in the absence of RECIST progression.

Categorization of BoR will be based on the RECIST criteria using the following order of response categories: CR, PR, SD, NED (applies only to those patients entering the study with no disease at baseline), PD and NE. Patients entering the study with no measurable disease at baseline who would qualify for CR are considered as SD and summarized separately as “stable disease (complete response without measurable disease)”.

BoR will be determined programmatically from the overall visit response using BICR data. In addition, this will also be reported using investigator-recorded assessment.

For determination of a best response of SD, the earliest of the dates contributing towards a particular overall visit assessment will be used. SD should be recorded at least 7 weeks (ie, 8 weeks minus 1 week to allow for an early assessment within the assessment window), after randomisation. For CR/PR, the initial overall visit assessment which showed a response will use the latest of the dates contributing towards a particular overall visit assessment.

For patients whose progression event is death, BoR will be calculated based on data up until the last evaluable RECIST assessment prior to death.

For patients who die with no evaluable RECIST assessments, if the death occurred ≤ 17 weeks (ie, 16 weeks +1 week to allow for a late assessment within the assessment window) after randomisation then BoR will be assigned to the PD category. For patients who die with no evaluable RECIST assessments, if the death occurred > 17 weeks (ie, 16 weeks +1 week) after randomisation then BoR will be assigned to the NE category.

Progression events that have been censored due to them being more than two missed visits after the last evaluable assessment will not contribute to the BoR derivation.

A patient will be classified as a responder if the RECIST criteria for a CR or PR are satisfied at any time following randomisation, prior to RECIST progression and prior to starting any subsequent cancer therapy.

3.2.8 Objective response rate

For each treatment group, the ORR is the number of patients with a BoR of CR and PR according to the BICR data divided by the number of patients in the treatment group with measurable disease at baseline where 'measurable' is defined by the BICR data. Only patients with measurable disease at baseline can achieve an objective response of CR or PR.

As supportive summaries, duration and time to onset of objective response in patients with an objective response (derived using BICR data) will be calculated using a Kaplan-Meier technique.

Duration of response will be defined as the time from the date of first documented response until date of documented progression or death in the absence of disease progression. The end of response should coincide with the date of progression or death from any cause used for the PFS endpoint (using BICR data). The time of the initial response will be defined as the latest of the dates contributing towards the first visit response of PR or CR. If a subject does not progress following a response, then the patient will be censored at the same timepoint that was used for the censored PFS analysis.

Time to onset of objective response will be defined as the time from randomisation to the date of first documented response.

ORR, duration of response and time to onset of objective response will also be calculated using investigator-recorded assessment, with 'measurable' disease at baseline defined according to investigator assessment.

3.2.9 Disease control rate

The DCR is defined as the percentage of patients who have at least one visit response of CR or PR or have demonstrated SD or NED for at least 15 weeks (ie, 16 weeks minus 1 week to allow for an early assessment within assessment window) prior to any evidence of

progression. In the case of SD and NED, follow-up assessments must have met the SD or NED criteria for a minimum interval of 15 weeks following randomisation. This will be calculated using BICR data, in addition to investigator-recorded assessment.

CCI [REDACTED]
[REDACTED]
[REDACTED]

[REDACTED]

- | [REDACTED]
- | [REDACTED]
- | [REDACTED]
- | [REDACTED]
 - | [REDACTED]
 - | [REDACTED]
 - | [REDACTED]
 - | [REDACTED]
 - | [REDACTED]
- | [REDACTED]

CCI [REDACTED]
[REDACTED]

CCI [REDACTED]
[REDACTED]

CCI [Redacted]

[Redacted]

[Redacted]

CCI [Redacted]

[Redacted]

[Redacted]

CCI [Redacted]

[Redacted]

CCI [Redacted]

[Redacted]	[Redacted]	[Redacted]	[Redacted]
------------	------------	------------	------------

[Redacted]	[Redacted]	[Redacted]	CCI [Redacted]
[Redacted]	[Redacted]	[Redacted]	
[Redacted]	[Redacted]	[Redacted]	
[Redacted]	[Redacted]	[Redacted]	
[Redacted]	[Redacted]	[Redacted]	

[Redacted]

CCI
[Redacted]

[Redacted]

[Redacted]

[Redacted]

CCI	

CCI [Redacted]

[Redacted]

[Redacted]

[Redacted]

[Redacted]

[Redacted]

[Redacted]

[Redacted]

[Redacted]

CCI [Redacted]

[Redacted]

[Redacted]

CCI [Redacted]

[Redacted]

[Redacted]

[Redacted]

[Redacted]

[Redacted]

[Redacted]

[Redacted]

[Redacted]

CCI

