3.1.4 Independent review

A planned BICR of all radiological imaging data will be carried out using modified RECIST version 1.1 and these data will be used for the interim and primary analyses of PFS. All radiological scans for all patients (including those at unscheduled visits, or outside visit windows) will be collected on an ongoing basis and sent to an AstraZeneca appointed Contract Research Organisation (PAREXEL Imaging) for central analysis. Prior radiotherapy and location of screening biopsy lesion reports will also be provided to the BICR to allow the selection of appropriate TLs. The imaging scans will be reviewed by 2 independent radiologists using modified RECIST 1.1 and will be adjudicated, if required. For each patient, the BICR will define the overall visit response (ie, the response obtained overall at each visit by assessing TLs, NTLs and new lesions) data (for patients with TLs at baseline: CR, PR, SD, PD, NE; for patients with NTLs only: CR, SD, PD or NE; for patients with no disease identified at baseline: PD, NED, NE). If a patient has had a tumour assessment that cannot be evaluated then the patient will be assigned a visit response of NE (unless there is evidence of progression in which case the response will be assigned as PD).

RECIST assessments/scans contributing towards a particular visit may be performed on different dates and for the central review the date of progression will be determined based on the earliest of the scan dates of the component that triggered the progression, either for the adjudicated reviewer selecting PD or of the first reviewer where both select PD as time-point response and there is no adjudication.

Results of this independent review will not be communicated to Investigators and the management of patients will be based solely upon the results of the modified RECIST 1.1 assessment conducted by the Investigator.

On an ongoing basis, patients who are determined to have progressed according to modified RECIST 1.1 criteria by the investigator will have scans centrally reviewed for confirmation of objective disease progression. Radiological scans will only be sent for BICR up until the date of RECIST progression determined by the investigator. However, if disease progression is not confirmed at BICR, an additional RECIST assessment will be requested at the next scheduled RECIST visit. After the final PFS analysis, BICR of scans will no longer be required, regardless of progression status.

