4.2.8 Best objective response and objective response rate

For each treatment group, BoR as defined in Section 3.2.7 will be summarised by n (%) for each category (CR, PR, SD, NED, PD, NE) based on the BICR data. This will also be summarised based on the investigator-assessed data. No formal statistical analyses are planned.

ORR as defined in Section 3.2.8 will be summarised descriptively, ie, number of patients (%) by treatment group, and using logistic regression, based on the BICR data, in patients in the FAS (ITT population) with measurable disease at baseline defined according to BICR. The results of the analysis will be presented in terms of an odds ratio together with its associated profile likelihood 95% CI and p-value (based on twice the change in log-likelihood resulting from the addition of a treatment factor to the model). If there are not enough responses for a meaningful analysis using logistic regression, then a Fisher's exact test will be presented.

ORR will also be summarised based on the investigator-assessed data in the FAS (ITT population) with measurable disease at baseline defined according to investigator assessment using the same methods as for the BICR data. Any patients who experienced CR or PR which was first observed whilst receiving subsequent therapy after discontinuation of olaparib will be identified and not treated as responders per definition of BoR in Section 3.2.7.

In addition, the duration and time to onset of objective response in patients with objective response (by BICR and by investigator assessment) will be summarised by treatment group.

95% confidence intervals for median duration and median time to onset of objective response in patients with objective response (by BICR and by investigator assessment) calculated using the Kaplan Meier method will be presented by treatment group.

BoR will be presented in a by-patient listing. In addition, a listing will be prepared including objective responders (confirmed CR or PR) only.

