4.2.9 Disease control rate

The DCR as defined in Section 3.2.9 will be summarised (ie, n, %) by treatment group. The DCR will be presented based on the BICR data and also the investigator recorded data.

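### DCR in SAP 3.2.9 has no cut at subsequent cancer therapy, so a CR or PR that the plan bars from BoR and ORR can still make a patient a disease-control success

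*SAP*

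**What the plan says.** DCR is built on individual visit responses. Section 3.2.9 opens: "The DCR is defined as the percentage of patients who have at least one visit response of CR or PR". The alternative route is SD or NED, for which "follow-up assessments must have met the SD or NED criteria for a minimum interval of 15 weeks following randomisation". The only limit named is progression. Section 4.2.9 adds no other: "The DCR as defined in Section 3.2.9 will be summarised (ie, n, %) by treatment group".

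Best objective response is cut differently. Section 3.2.7 says: "It is the best response a patient has had following randomisation but prior to starting any subsequent cancer therapy". It repeats the limit for responders, whose CR or PR must come "prior to RECIST progression and prior to starting any subsequent cancer therapy". ORR inherits it, because under section 3.2.8 "the ORR is the number of patients with a BoR of CR and PR according to the BICR data". Section 4.2.8 restates it: patients whose CR or PR was "first observed whilst receiving subsequent therapy after discontinuation of olaparib will be identified and not treated as responders".

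Scans after a switch are foreseen. Section 1.2 keeps patients who stop without radiological progression on the scan schedule, leaves further treatment to the investigator and anticipates platinum re-treatment. Section 3.1.4 adds that "if disease progression is not confirmed at BICR, an additional RECIST assessment will be requested at the next scheduled RECIST visit".

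**The concern.** DCR at week 16 by BICR is a listed secondary objective (section 1.1), meant to compare olaparib maintenance with placebo. If a response first seen on next-line treatment counts, DCR partly describes that treatment and not the randomised one. The same report would then hold two rules for the same scan: a PR that is no response for BoR and ORR, yet is enough on its own for disease control. If patients on one arm switch earlier than on the other, the arms are also affected unequally.

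**Working it through.** **The plan's own figure.** The only number in the DCR definition is the minimum SD/NED duration: 16 weeks − 1 week = 15 weeks, as stated.

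**Rules side by side.**

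| Quantity | SAP section | Built on | Ends at progression | Ends at subsequent therapy |
|---|---|---|---|---|
| BoR | 3.2.7 | Visit responses | Yes | Yes |
| ORR | 3.2.8, 4.2.8 | BoR | Yes | Yes |
| DCR, CR/PR part | 3.2.9, 4.2.9 | Visit responses | Unclear from the sentence | Not stated |
| DCR, SD/NED part | 3.2.9, 4.2.9 | Visit responses from randomisation | Yes | Not stated |

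DCR does not refer to BoR or responder status, so it does not inherit their cut. The grammar also leaves open whether the progression limit governs the CR/PR part or only the SD/NED part.

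**Can the case arise?** Two routes follow from the SAP's rules.

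1. BICR version. The investigator calls progression at week 8. BICR does not confirm it. Management follows the investigator (3.1.4), so the patient may start chemotherapy, and another scan is requested at week 16. If BICR reads PR, the patient is a DCR success under 3.2.9 but not a responder under 3.2.7. If BICR reads SD, having read SD at week 8, the SD has run past week 15 and also counts.
2. Either version. The patient stops for another reason, such as symptomatic deterioration (3.1.2), without RECIST progression, starts new therapy and stays on the scan schedule. The same two outcomes follow.

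Route 1 does not affect the investigator version, where the week-8 progression already ends the SD/NED period. In both routes SD is usually carried past the switch; it is first seen afterwards only if week 8 was missed or not evaluable.

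**Scale per patient.** Section 1.3 plans about 145 patients at 3:2, and Table 1 analyses DCR in the FAS.

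- Olaparib: 145 × 3/5 = 87; one patient = 1/87 = 1.1 points.
- Placebo: 145 × 2/5 = 58; one patient = 1/58 = 1.7 points.
- Assumed 1, 3 or 6 reclassified placebo patients: 1/58 = 1.7, 3/58 = 5.2, 6/58 = 10.3 points.

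The counts 1, 3 and 6 are assumptions; the SAP gives none.

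**The case against.** The strongest reply is that the primary endpoint also ignores subsequent therapy. Section 3.2.1 counts PFS events whether or not the patient has moved to another anticancer treatment. The SD/NED part of DCR is close to a week-15 landmark of that endpoint, so leaving it uncut is a defensible choice, and adding the cut makes DCR differ from PFS. This stands for SD and NED. It does not rescue CR and PR, where the SAP's stated rule is exclusion. Section 3.2.1 also states its choice openly, while 3.2.9 is silent.

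The stakes are small, and that stands too. DCR is reported as n (%) only, does not appear in Table 10 or Table 11, and is outside the testing hierarchy of section 4.2.1. Section 4.2.10 tabulates subsequent therapy given before progression, and the attrition-bias analysis in 4.2.2.1 censors PFS at it, so early switching is partly visible elsewhere. Neither output tells the reader who counted towards DCR.

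A reader might go further and infer that the plan orders next-line results to be credited to the randomised arm. It does not; this is the literal effect of an omission.

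**Conclusion.** The contradiction is clear for CR and PR: following 3.2.9 as written, a patient can reach disease control through a response that three other sections say is not a response. For SD and NED it is an unstated choice that should be made explicit.

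The size cannot be derived from the SAP. It is 1.7 points per reclassified placebo patient and 1.1 per olaparib patient at the planned arm sizes, times an unknown number of patients who switch before RECIST progression in the data set used. It is tempting to take week-8 progression rates from the assumed PFS medians, multiply by an assumed BICR non-confirmation rate and add the product to the assumed progression-free rates. That fails twice. Those medians describe BICR-based PFS, so patients counted as progressed are already confirmed by BICR; and the progression-free rates already include patients who switched without BICR progression.

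The direction is not settled either. If placebo patients switch earlier, the arm difference would narrow, against olaparib; the documents give no switching data to show this. PFS, OS and type I error are unaffected.

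**What to change.** In section 3.2.9, require the CR or PR to occur "prior to RECIST progression and prior to starting any subsequent cancer therapy", as in 3.2.7. This also settles whether progression limits the CR/PR part. Apply the same cut to SD and NED, so that DCR describes the randomised treatment: a patient who starts subsequent therapy before week 15 without a prior CR or PR is then not a success. Use the rule in both the BICR and investigator versions.

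Report per arm how many patients qualify only through scans after the switch, so that the result under either rule can be read off.

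Section 4.2.1 records that DCO1 took place in January 2019, and the study was to be unblinded for that analysis, so record the change as made after unblinding. For any DCR already produced, state which rule was programmed.

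The cost is one clause and one programming condition; start dates of subsequent therapy are already collected for TFST (3.2.4). DCR may fall slightly and will no longer follow the PFS rule, which the text should say.
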